1.0 EXECUTIVE SUMMARY

1.1 Title

A Clinical Evaluation of the Medtronic Resolute Onyx Zotarolimus-Eluting 2.0 mm Stent

1.2 Objective

The purpose of this trial is to assess the safety and efficacy of the Resolute Onyx Zotarolimus-Eluting Coronary Stent System for the treatment of *de novo* lesions in native coronary arteries that allows the use of a 2.0 mm diameter stent.

1.3 Design

Single arm, open label multicenter trial

1.4 Study Device

Medtronic Resolute Onyx 2.0 mm Zotarolimus-Eluting Coronary Stent System (Resolute Onyx 2.0 mm stent)

1.5 Endpoints

1.5.1 Primary Endpoint

Target Lesion Failure (TLF) at 12-months post-procedure, defined as Cardiac Death, Target Vessel Myocardial Infarction (TVMI) (Q wave or non-Q wave) or Target Lesion Revascularization by percutaneous or surgical methods.

1.5.2 Key Secondary Clinical Endpoints

- Cardiac Death
- Target Vessel Myocardial Infarction (TVMI)
- Cardiac Death and TVMI
- Major Adverse Cardiac Event (MACE)
- Target Lesion Failure (TLF)
- Target Vessel Failure (TVF)
- Stent Thrombosis (ST)

1.5.3 Secondary Imaging Endpoint

- Ischemia assessment per Myocardial Perfusion Imaging (MPI) for subjects who had MPI at baseline and consent to a follow up MPI

1.5.4 Secondary Angiographic Endpoints

- Late Lumen Loss (LLL)
- Binary Angiographic Restenosis (BAR) rate (defined as $\geq 50\%$ diameter stenosis (DS))
- Percent Diameter Stenosis (% DS)

RESOLUTE Onyx 2.0 mm Clinical Study**CONFIDENTIAL - May not be reproduced without written permission from Medtronic**

1.6 Subject population

At least 100 subjects with ischemic heart disease due to *de novo* stenotic lesions within native coronary arteries that meet the eligibility criteria and sign the informed consent form will be asked to participate in this trial. All subjects who consent will be asked to participate in the 13 month angiographic subset until at least 20 subjects have been enrolled in this subset. Subjects may receive treatment in up to two lesions, if the lesions are located in separate target vessels. Core size lesions should be treated with the currently approved Resolute Integrity stent.

The trial will be conducted at a maximum of 25 investigational sites within the United States (US) and Japan. Sites are allowed to enroll a maximum of 20 subjects per site or until study enrollment has been completed, whichever comes first. The expected time of participation in the trial for each subject is three years.

1.6.1 Key Inclusion Criteria

- Subject has clinical evidence of ischemic heart disease. For single vessel disease: stable or unstable angina alone is sufficient. For multi-vessel treatment: a positive functional study or FFR to demonstrate functional need in 2.0 mm small vessel.
- Subject has either a single target lesion suitable for treatment with a Resolute Onyx 2.0 mm stent, or two target lesions located in separate target vessels with at least one suitable for treatment with a Resolute Onyx 2.0 mm stent

See [Section 4.4](#) for a detailed description for all Inclusion Criteria.

1.6.2 Key Exclusion Criteria

- Evidence of an acute MI within 72 hours of the intended trial procedure
- Planned PCI of any vessel within 30 days post-index procedure and/or planned PCI of the target vessel(s) within 12 months post-procedure. (No staged procedures).

Note: Refer to [Table 2](#) in [Section 4.4.5](#) for additional procedure criteria for planned PCI of the target and other (non-target) vessel(s).

See [Section 4.4](#) for a detailed description for all Exclusion Criteria.

1.7 Schedule of Follow up Assessments

Subject Contact (the subject will be assessed by telephone, e-mail, and/or office visit) at:

- 30 days
- 6 months (subjects that did not have baseline MPI performed)
- Annually 12 months, 2 and 3 years (all subjects)

Clinic Visit (the subject must return to the same investigational site where the index procedure was performed) at:

- 6 months (MPI assessment – subjects with baseline MPI performed and consent to follow-up MPI only)
- 13 Months (angiographic assessment – 2.0 mm Angio subset subjects only)

RESOLUTE Onyx 2.0 mm Clinical Study**CONFIDENTIAL - May not be reproduced without written permission from Medtronic**

- Angiography should be performed for any post-procedure clinical event (e.g., MI) to determine if the event is attributable to the target vessel or a non-target vessel. The reason for any repeat angiography (either clinically driven or non-clinically driven) must be documented on the CRF.

Revascularization should only be conducted when ischemic symptoms are found by an objective measurement and stenosis alone does not justify revascularization.

1.8 Statistical Methods

The primary safety endpoint of Target Lesion Failure (TLF) at 12 months post-procedure will be compared to a performance goal derived from outcomes of other Drug Eluting Stents (DES). The TLF performance goal of 19% at 12-months is based on US approved 2.25 mm drug-eluting stent data. The RESOLUTE ONYX 2.0 mm Study design with 100 subjects yields more than 80% power, assuming a one-sided type 0.05 level of significance and 10% loss to follow up.

RESOLUTE Onyx 2.0 mm Clinical Study**CONFIDENTIAL - May not be reproduced without written permission from Medtronic**

2.0 INTRODUCTION

2.1 Background

Drug eluting stents have demonstrated superiority over bare metal stents in small vessels^{1,2,3} and have been shown to be most effective in reducing restenosis in high risk populations, such as those with small reference vessel diameters^{4,5}. A large meta-regression analysis of 31 randomized trials has demonstrated that the clinical benefit of DES increases as the risk profile of the subject increases, without affecting safety⁶. Therefore, the greatest benefit in reducing revascularizations and most cost-effective use of DES are seen in challenging lesions, such as small vessels⁷. Accordingly, Medtronic Vascular has developed a Resolute Onyx 2.0 mm device specifically for the treatment of small stenotic coronary arteries.

Currently, there are approved 2.0 mm bare metal stents, but no approved 2.0 mm DES in the US. A clinical trial is being conducted to demonstrate that the Resolute Onyx 2.0 mm TLF rate is significantly lower than the performance goal estimated from the DES TLF rate in the treatment of small vessel lesions. The successful demonstration of a TLF significantly below the DES TLF Performance Goal would additionally be significantly below the estimated 12-month TLF rates for BMS and POBA in small vessel stenotic coronary disease.

2.2 Study Device Name and Description

The investigational device being evaluated in this clinical trial is the Medtronic Resolute Onyx 2.0 mm Zotarolimus-Eluting Coronary Stent System.

The following is a summary of the Resolute Onyx Stent System. More detailed information regarding clinical indications, contraindications, warnings and precautions, preclinical testing and materials in contact with tissues or body fluids, can be found in the ‘Instructions for Use’ (IFU).

The Medtronic Resolute Onyx Zotarolimus-Eluting Coronary Stent System is comprised of four main components:

1. Stent Platform- Onyx Bare Metal Stent
2. Stent Delivery System - Resolute Onyx Delivery System RX
3. Zotarolimus – Anti-proliferative drug component/active pharmaceutical ingredient
4. Polymer – BioLinx™ Polymer System

2.2.1 Stent

The Resolute Onyx stent is similar in design to the Resolute Integrity stent and utilizes the same continuous sinusoid manufacturing technology.

RESOLUTE Onyx 2.0 mm Clinical Study
CONFIDENTIAL - May not be reproduced without written permission from Medtronic

Table 1: Resolute Onyx Stent Platform

Resolute Onyx	
Material Composition	Cobalt Alloy-shell Platinum/Iridium- core
Appearance	

The stent is manufactured from a composite wire which has an outer shell and an inner core. The outer shell which is in contact with the vessel is of the identical cobalt chromium alloy used for the Resolute Integrity stent. The inner core material is a Platinum/Iridium alloy intended to enhance radiopacity. The stent design has been modified slightly to provide a lower crossing profile and thus, improved deliverability over predicate products.

2.2.2 Stent Delivery System

The Medtronic Resolute Onyx Zotarolimus-Eluting Coronary Stent System consists of a balloon-expandable intracoronary drug-eluting stent pre-mounted on a Rapid Exchange (RX) stent delivery system. The delivery system has two radiopaque markers to aid in the placement of the stent during fluoroscopy and is compatible with 0.014 inch (0.36 mm) guidewires and 5 Fr (1.42 mm/0.056 in) minimum inner diameter guide catheters. The Resolute Onyx RX delivery system (Figure 1) has an effective length of 140 cm.

[figure not shown]

Figure 1: Resolute Onyx RX Delivery System (with Stent)

2.2.3 Zotarolimus Drug Substance

The therapeutic agent utilized in the Medtronic Resolute Onyx Zotarolimus-Eluting Coronary Stent System is zotarolimus, a licensed proprietary chemical entity from Abbott Laboratories, and is also identical to the predicate Endeavor Resolute and Resolute Integrity products. Zotarolimus is a tetrazole-containing macrocyclic immunosuppressant. The suggested mechanism of action of zotarolimus is to bind to FKBP12, leading to the formation of a trimeric complex with the protein kinase mTOR (mammalian target of rapamycin), inhibiting its activity. Inhibition of mTOR results in the inhibition of protein phosphorylation events associated with translation of mRNA and cell cycle control. The zotarolimus drug in the Resolute Onyx Stent is intended to reduce the incidence of restenosis in coronary interventions. The Resolute Onyx

RESOLUTE Onyx 2.0 mm Clinical Study**CONFIDENTIAL - May not be reproduced without written permission from Medtronic**

Stent has a nominal drug dose of approximately 1.6 μ g zotarolimus per mm² of the stent surface, which is identical to that of Endeavor Resolute and Resolute Integrity.

2.2.4 BioLinx Polymer

The Resolute Onyx stent is comprised of a bare metal stent with a Parylene C primer coat and a coating that consists of a blend of the drug zotarolimus and the BioLinx polymer system. BioLinx is a blend of the Medtronic proprietary components C10 (a copolymer of butyl methacrylate and vinyl acetate) and C19 (a terpolymer containing hexyl methacrylate, vinyl pyrrolidinone, and vinyl acetate), and PVP (polyvinyl pyrrolidone). The Resolute Onyx stent uses the same drug coating formulation, drug dose density and spray processing steps as the predicate Resolute Integrity product.

2.3 Intended Use

The Resolute Onyx 2.0 mm Stent System is intended to improve coronary luminal diameters in subjects with symptomatic ischemic heart disease due to *de novo* stenotic lesion(s) contained within a vessel diameter that allows the use of a 2.0 mm diameter stent.

RESOLUTE Onyx 2.0 mm Clinical Study
CONFIDENTIAL - May not be reproduced without written permission from Medtronic

3.0 CLINICAL TRIAL OBJECTIVES

The purpose of this trial is to assess the safety and efficacy of the Medtronic Resolute Onyx 2.0 mm Zotarolimus-Eluting Coronary Stent System for the treatment of *de novo* lesions in native coronary arteries with a reference vessel diameter (RVD) that allows the use of a 2.0 mm stent.

3.1 Primary Endpoint(s)

Target lesion failure (TLF) at 12-months post-procedure, defined as cardiac death, target vessel myocardial infarction (TVMI) (Q wave or non-Q wave) or clinically-driven target lesion revascularization (TLR) by percutaneous or surgical methods.

3.2 Key Secondary Endpoint(s)

Secondary endpoints of this trial include the following:

Clinical Endpoints:

- Acute Success (Device, Lesion, Procedure)
- The following secondary endpoints will be assessed at hospital discharge, 30 days, 6 months, and 12 months post-procedure, and annually thereafter through year 3:
 - o Cardiac Death
 - o Target Vessel Myocardial Infarction (TVMI)
 - o Cardiac Death and TVMI
 - o Major Adverse Cardiac Event (MACE)
 - o Defined as death, myocardial infarction (Q wave and non-Q wave), emergent coronary bypass surgery, or clinically-driven repeat target lesion revascularization by percutaneous or surgical methods
 - o Target Lesion Failure (TLF)
 - o Target Vessel Failure (TVF)
 - o Stent Thrombosis (ST)

Imaging Endpoint:

- The following secondary endpoint will be assessed at 6 months for subjects who received Myocardial Perfusion Imaging (MPI) per standard care at baseline:
 - o Percentage of Myocardium with Reversible Ischemia per Myocardial Perfusion Imaging

Other clinical parameters of stress testing will be collected at baseline and at follow-up testing to assess change following the stenting procedure. These parameters include stress induced angina symptoms, incidence of ST-depression, and exercise capacity.

RESOLUTE Onyx 2.0 mm Clinical Study**CONFIDENTIAL - May not be reproduced without written permission from Medtronic**

Angiographic Endpoints:

- The following Angiographic Endpoints will be assessed at 13 months post-procedure (for at least 20 subjects):
 - Late Lumen Loss (LLL)
 - Binary Angiographic Restenosis (BAR) rate (defined as >50% diameter stenosis (DS))
 - Percent Diameter Stenosis

RESOLUTE Onyx 2.0 mm Clinical Study**CONFIDENTIAL - May not be reproduced without written permission from Medtronic**

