4.0 CLINICAL TRIAL DESIGN

The Medtronic RESOLUTE ONYX 2.0 mm Clinical Trial is a single arm, open label, multi-center trial enrolling at least 100 subjects with ischemic heart disease attributable to stenotic lesions of the native coronary arteries that are amenable to percutaneous treatment with a Resolute Onyx 2.0 mm stent. At least 20 subjects will be enrolled to receive an angiographic follow up at 13 months.

Subjects may receive treatment of one or two lesions, one lesion per target vessel, for a maximum of two target vessels. Only one lesion may be treated in a single target vessel. All treatment with the study stents is to be performed during a single index procedure. Refer to [Table 2](#) for additional stenting criteria.

In the event of one lesion to be treated with a 2.0 mm study stent and another lesion to be treated with a core size (2.25 mm - 4.0 mm) Resolute Integrity stent, the subject should be treated first with the core-sized stent. If the treatment of the first lesion fails or if the subject becomes unstable *before* a 2.0 mm study stent is attempted (stent introduced into guide catheter), the subject will not be enrolled, will not be followed, and will not be included in the primary analysis of this trial. Another subject should be enrolled to replace this subject for the primary analysis. If the treatment with the 2.0 mm study stent is attempted (stent introduced into guide catheter) but not implanted, the subject will be considered part of the Intention-to-Treat population (ITT) and will be followed through the 12 month endpoint and will be included in the primary analysis of this trial.

For subjects who have more than one lesion planned for treatment, a positive functional study or FFR should be performed in the vessel expected to receive the 2.0 mm study stent to demonstrate the functional need for treating such a lesion.

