5.6.2 Follow-up Data Collection Procedure

The date for the 30-day follow up should be calculated by adding 30 days to the index procedure date (e.g. stent implant on December 5th, 30 day follow-up on January 4th). The dates for the 6 month, 12 month, 13 month and annual (years 2-3) follow-up assessments should be calculated

RESOLUTE Onyx 2.0 mm Clinical Study
CONFIDENTIAL - May not be reproduced without written permission from Medtronic

using the anniversary date of the index procedure (e.g., stent implant on December 5th, 6 month follow-up on June 5th, 12 month and annual thereafter on December 5th). If the procedure was performed on the 31st and the follow-up month has only 30 days, the anniversary should be calculated to the first day of the next month. Visit window calculations will be provided for each subject through the electronic data capture (EDC) system.

Table 7: Subject Follow-up Time Window

Example: Date of implant: 5/DEC/2014

Contact Period	Visit Target Date	Visit Window Dates	
		From	To
30 Day \pm 5 days	4/JAN/2015	30/DEC/2014	9/JAN/2015
6 Month \pm 14 days	5/JUN/2015	22/MAY/2015	19/JUN/2015
12 Month \pm 30 days	5/DEC/2015	5/NOV/2015	4/JAN/2016
13 Month \pm 14 days	5/JAN/2016	22/DEC/2015	19/JAN/2016
2 Year \pm 30 days	5/DEC/2016	5/NOV/2016	4/JAN/2017
3 Year \pm 30 days	5/DEC/2017	5/NOV/2017	4/JAN/2018

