5.7 Subject Withdrawal / Removal from the Trial

A trial subject has the right to discontinue participation at any time without penalty or loss of benefits to which the subject is otherwise entitled. A withdrawn subject will be treated according to standard of medical care and will not be replaced. Subjects will be included in the analyses up to the time that consent was withdrawn.

If a subject decides to withdraw from the trial, the investigator will document the reason for withdrawal and indicate any rationale for the withdrawal from the trial in the subject's file. Subjects may decide to withdraw from study follow up visits/contacts but consent to continue to allow data collection from their medical records.

Subject Lost-To-Follow-Up (LTFU) should be avoided as much as possible and investigators are urged to do their utmost best to maintain subject follow-up compliance. Contacting the subject's general practitioner or referring cardiologist should be considered in case the subject cannot be reached in order to obtain information about the subject's health status and documented in the subject's file. Continuous attempts throughout the three year follow-up period should be made to contact the subject, the subject's family or referring physician before documenting a subject LTFU. It is recommended that death study databases (SSDI) should be checked before subjects are considered LTFU.

RESOLUTE Onyx 2.0 mm Clinical Study
CONFIDENTIAL - May not be reproduced without written permission from Medtronic

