7.2 Sample Size Justification

If the 12-month TLF rate of the Resolute Onyx 2.0 mm stent is shown to be significantly less than 19%, then the trial will be considered to have met its primary objective. In other words, the assessment of TLF is a testing with the following null and alternative hypotheses:

$$H_0: \pi \geq 19\% \text{ vs. } H_1: \pi < 19\%,$$

where π is the true Resolute Onyx 2.0 mm stent 12-month TLF rate.

The assessment of the null hypothesis will be carried out at the one-sided 0.05 level of significance. Rejection of the null hypothesis indicates the Resolute Onyx 2.0 mm stent 12-month TLF rate is significantly below 19%.

Accounting for a 10% clinical loss to follow-up and one-sided 0.05 level of significance, a sample size of 100 subjects yields more than 80% power to reject the above null hypothesis in favor of the alternative, assuming the true Resolute Onyx 2.0 mm stent 12-month TLF rate is 9.4%.

RESOLUTE Onyx 2.0 mm Clinical Study
CONFIDENTIAL - May not be reproduced without written permission from Medtronic

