3.2.2. Key Secondary Endpoints

Secondary endpoints of this trial include the following:

Clinical Endpoints:

- Acute Success (Device, Lesion, Procedure)
- The following secondary endpoints will be assessed at hospital discharge, 30 days, 6 months, and 12 months post-procedure, and annually thereafter through year 3:
 - Cardiac Death
 - Target Vessel Myocardial Infarction (TVMI)
 - Cardiac Death and TVMI
 - Target Lesion Revascularization (TLR)
 - Major Adverse Cardiac Event (MACE)
Defined as death, myocardial infarction (Q wave and non-Q wave), emergent coronary bypass surgery, or clinically-driven repeat target lesion revascularization by percutaneous or surgical methods
 - Target Lesion Failure (TLF)
 - Target Vessel Failure (TVF)
 - Stent Thrombosis (ST)

Imaging Endpoint:

- The following secondary endpoint will be assessed at 6 months for subjects who received Myocardial Perfusion Imaging (MPI) per standard care at baseline:
 - Percentage of Myocardium with Reversible Ischemia per Myocardial Perfusion Imaging

Other clinical parameters of stress testing will be collected at baseline and at follow-up testing to assess change following the stenting procedure. These parameters include stress induced angina symptoms, incidence of ST-depression, and exercise capacity.

Angiographic Endpoints:

- The following Angiographic Endpoints will be assessed at 13 months post-procedure (for at least 20 patients):
 - Late Lumen Loss (LL)
 - Binary Angiographic Restenosis (BAR) rate (defined as >50% diameter stenosis (DS))
 - Percent Diameter Stenosis

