Appendix II: Follow-up Visit Windows for Endpoint Analyses

Follow-up interval	Study Time Window Post Procedure
30 days	30±5 days
6 months	180 ±14 days
12 months*	360 ±30 days
13 months (2.0mm Angio subset)	390 ±14 days
24 months	720 ±30 days
36 months	1080 ±30 days

*12 month Clinical Follow up must occur at least 1 day prior to the 13 month Angiographic Follow up

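### The angiographic endpoints are stated for at least 20 subjects assessed, but the plan secures only 20 enrolled, and the SAP's 13-month window misses the last 3 to 7 on-time days

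*Protocol*

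**What the plan says.** **Number of subjects.** Protocol 3.2, on late lumen loss, binary restenosis and percent diameter stenosis, reads: "The following Angiographic Endpoints will be assessed at 13 months post-procedure (for at least 20 subjects". SAP 3.2.2 has the matching line: "The following Angiographic Endpoints will be assessed at 13 months post-procedure (for at least 20 patients". The recruitment rule is in Protocol 1.6, where consenting subjects are asked to join "until at least 20 subjects have been enrolled in this subset"; SAP 3.1 repeats it. Protocol 4.0 also treats the number as an enrolment count: "At least 20 subjects will be enrolled to receive an angiographic follow up at 13 months".

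**Loss.** The only loss rate in either document belongs to the primary endpoint. Protocol 7.2 has "Accounting for a 10% clinical loss to follow-up", and SAP 3.3 agrees. Neither document gives a rate or an allowance for the angiographic subset. On withdrawal, Protocol 5.7 says: "A withdrawn subject will be treated according to standard of medical care and will not be replaced". Under Protocol 5.4.6, subjects in whom the study stent could not be implanted are followed only through 12 months, which is before the 13-month angiogram.

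**Visit window.** Protocol 5.6.2 says: "The dates for the 6 month, 12 month, 13 month and annual (years 2-3) follow-up assessments should be calculated" from the anniversary of the index procedure. Table 6 allows 14 days either side of the 13-month date, and Table 7 works an example. SAP Appendix II, headed "Follow-up Visit Windows for Endpoint Analyses", gives the 13-month angiographic visit as day 390 plus or minus 14.

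**The concern.** The same number serves as the count enrolled and as the count assessed. Both can be true only if everyone returns for a repeat catheterisation, or if more than 20 are enrolled, which the rule permits but does not require. A reader of the endpoint section would expect at least 20 angiograms; the plan does not secure that.

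The window is a second, independent gap. Sites follow the protocol calendar, and the analysis follows Appendix II. An angiogram can be on time for the site and fall outside the window listed for endpoint analyses. In a subset of 20, each angiogram is 5% of the data, so its handling should be settled before the data are seen.

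**Working it through.** The documents give no derivation of the 20, so there is no calculation to reproduce. Two checks apply.

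**1. Enrolled versus assessed**

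Inputs: n = 20, the minimum subset (Protocol 1.6 and 4.0, SAP 3.1); d = 0.10, borrowed from Protocol 7.2, where it describes clinical loss for the 12-month primary endpoint. Its use for a 13-month angiogram is an assumption. Subjects are taken to be lost independently.

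- Expected evaluable: n × (1 − d) = 20 × 0.90 = 18.
- Chance that all 20 return: (1 − d)^n = 0.90^20 = 0.122, or 12%.
- Chance of fewer than 20: 1 − 0.122 = 0.878, or 88%.
- For a less favourable assumed loss of 20%: 20 × 0.80 = 16 expected, and 0.80^20 = 0.012, or 1%.

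Effect on precision, as the half-width of a two-sided 95% t interval for a mean such as late loss, in SD units, t(0.975, n − 1)/√n:

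- n = 20: 2.093/4.472 = 0.468
- n = 18: 2.110/4.243 = 0.497

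The interval widens by about 6% (0.497/0.468 = 1.06).

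**2. Protocol window versus SAP window**

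From Protocol Table 7, with implant on 5 December 2014 as day 0:

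| | Earliest | Target | Latest |
|---|---|---|---|
| Protocol (Table 7) | 22 Dec 2015 = day 382 | 5 Jan 2016 = day 396 | 19 Jan 2016 = day 410 |
| SAP Appendix II | day 376 | day 390 | day 404 |

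Days 405 to 410 are on time under the protocol and outside the SAP window: 6 of 29 days. At the other end, days 376 to 381 are early for the site but inside the SAP window.

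The size of the gap depends on the implant date. If the calendar target is day T, the uncovered days number (T + 14) − 404 = T − 390. Thirteen calendar months are 365 or 366 days plus one further month. For every implant date from 2014 through 2017, T lies between 393 and 397, so the gap is 3 to 7 of 29 days, with a mean of 5.7. The cause is that Appendix II counts months as 30 days (13 × 30 = 390), whereas the protocol counts calendar months.

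No other SAP rule closes the gap. The denominator rule in SAP 6.1 is written for clinical events and refers only to the lower edge of the window.

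**The case against.** The strongest reply is that nothing here is miscalculated and nothing depends on it. The secondary endpoints are descriptive (Protocol 7.5, SAP 6.3), no hypothesis or success rule uses the 20, and the change in precision is slight. The number in parentheses can also be read as the size of the subset, in line with Protocol 4.0, and not as a promise of evaluable angiograms. The point about impact stands in full. The reading is possible, but it is not what the endpoint sentence says, and a short rewording would remove the doubt.

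Three stronger readings are tempting, and the documents do not support them:

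- **That recruitment to the subset closes at 20.** The rule sets a floor. The obligation to ask subjects ends there, but nothing forbids a larger subset, so 18 describes the minimum-enrolment case only.
- **That the trial itself expects 10% of angiograms to be lost.** The 10% is 12-month clinical loss, and that follow-up can be done by telephone or e-mail. The rate for an invasive return visit is not given and could differ.
- **That the SAP discards angiograms taken after day 404.** It never says so. If the clinical-event rule in SAP 6.1 were applied by analogy, late angiograms would be kept, because only the lower edge matters there. Any estimate of angiograms lost to the window would need an exclusion rule and a distribution of visit dates, and the documents supply neither.

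**Conclusion.** The point holds as two small inconsistencies. First, the endpoint sections state a minimum assessed, while the recruitment rule secures only a minimum enrolled, with no loss allowance and no replacement of withdrawn subjects. At minimum enrolment and an assumed 10% loss, about 18 would be evaluable, with a 12% chance that all 20 return. Second, protocol and SAP define the 13-month visit by different days: 3 to 7 of the 29 on-time days (6 in the Table 7 example) are not covered by the SAP window, and their handling is unspecified. The day mismatch is calendar arithmetic and rests on no assumption; the figure of 18 rests on the subset stopping at 20 and on the borrowed loss rate.

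The primary endpoint, its test and the power statement are not touched by this point. The consequence is limited to how the descriptive angiographic results are counted and described.

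**What to change.** 1. In SAP Appendix II, replace the 13-month entry with the protocol's 13-month anniversary date plus or minus 14 days. Every angiogram that is on time for the site is then inside the analysis window.
2. In Protocol 3.2 and SAP 3.2.2, restate the figure as at least 20 subjects enrolled in the angiographic subset, and add that the evaluable number is expected to be lower, about 18 if 10% are lost, with the 10% labelled as an assumption.

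The cost is one table cell and one phrase in each document. The stated angiographic sample becomes slightly less favourable; recruitment and the primary analysis do not change.
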